9.3 Withdrawal and Discontinuation

Any subject may voluntarily withdraw (i.e., reduce the degree of participation in the study) consent for continued participation and data collection. The reason for withdrawal will be recorded on the End of Study CRF. Assessments to be performed at the termination visit (including in cases of withdrawal or discontinuation) are described in Section 10.6 and Section 21.3.

Discontinuation (i.e., complete withdrawal from study participation) may be due to dropout (i.e., active discontinuation by subject) or loss to follow-up (i.e., discontinuation by subject without notice or action). Additionally, the investigator and sponsor have the discretion to discontinue any subject from the study if, in their judgment, continued participation would pose an unacceptable risk for the subject.

Subjects also will be withdrawn from treatment or discontinued from further study participation for the following reasons:

- The subject develops a confirmed high responder inhibitory antibody to FVIII (>5 BU by Nijmegen modification of the Bethesda assay) or a low responder inhibitory antibody (≤ 5 BU but ≥ 0.6 BU) that cannot be managed by the protocol-required prophylactic dosing.
- The subject experiences a severe anaphylactic reaction to BAX 855
- The subject requires therapy with another pegylated product (e.g., PEG-Interferon)
- The subject frequently misses administration of IP (misses more than 30% of planned prophylactic doses within any 3-month period)
- The subject is non-compliant with study procedures, in the opinion of the investigator and/or sponsor
- The subject uses his/her usual FVIII therapy following the baseline infusion
- The subject requires major emergency surgery during this study
- The subject experiences a life-threatening bleeding episode (e.g., any gastrointestinal hemorrhage or intracranial hemorrhage) requiring the use of a FVIII concentrate other than BAX 855
- The subject experiences severe trauma requiring extensive FVIII replacement therapy other than BAX 855

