10.6 Subject Completion/Discontinuation

A subject is considered to have completed the study when he/she ceases active participation in the study because the subject has, or is presumed to have, completed all study procedures according to the protocol (with or without protocol deviations).

Reasons for completion/discontinuation will be reported on the Completion/Discontinuation CRF, including: completed, screen failure, AE (e.g., death), discontinuation by subject (e.g., lost to follow-up [defined as 3 documented unsuccessful attempts to contact the subject], dropout), physician decision (e.g., pregnancy, progressive disease, non-compliance with IP/protocol violation(s), recovery), study terminated by sponsor, or other (reason to be specified by the investigator, e.g., technical problems). Regardless of the reason, all data available for the subject up to the time of completion/discontinuation should be recorded on the appropriate eCRF.

Every effort will be made to have discontinued subjects complete the study completion/termination visit. If the completion/termination visit is done as an additional, unscheduled visit, the assessment results shall be recorded with the completion/termination visit. If a subject terminates participation in the study and does not return for the completion/

termination visit, their last recorded assessments shall remain recorded with their last visit. The reason for discontinuation will be recorded, and the data collected up to the time of discontinuation will be used in the analysis and included in the clinical study report.

If additional assessments are required, the assessments shall be recorded separately. Assessments to be performed at the termination visit (including in cases of withdraw or discontinuation) can be found in Section 21.2 Detailed Flow Diagram of Study Procedures, Section 21.3 Schedule of Study Procedures and Assessments, and Section 21.4 Clinical Laboratory Assessments.

In the event of subject discontinuation due to an AE, clinical and/or laboratory investigations that are beyond the scope of the required study observations/assessments may be performed as part of the evaluation of the event. These investigations will take place under the direction of the investigator in consultation with the sponsor, and the details of the outcome may be reported to the appropriate regulatory authorities by the sponsor.

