The subject must not be actively bleeding.

Before any other study-specific procedures are carried out:

- PROs:
 - Haemo-SYM questionnaire
 - SF-36
 - EQ-5D
 - Physical Activity
 - Health Resource Use
- Return of subject diary and review and discuss entries with subject, including assessment of bleeding episodes and their treatment and type and duration of physical activity
- Physical examination, including body weight; Assessment of target joints; HJHS joint score

At the **pre-infusion** timepoint, the following assessments will be carried out:

- Vital signs (within 15 minutes of start of infusion)
- Laboratory Assessments:
 - FVIII, VWF Ag and TGA assays (within 30 minutes of start of infusion)
 - Hematology, clinical chemistry, and lipids
- Immunogenicity tests (within 30 minutes of start of infusion):
 - Inhibitory antibodies to FVIII (Nijmegen assay)
 - Binding antibodies (IgG and IgM) to FVIII, BAX 855, and PEG
 - Anti-CHO antibodies
- Additional blood draw for further exploratory testing

Infusion:

- Infusion of PK-guided prophylactic dose of BAX 855

Post-infusion:

- Laboratory Assessments:
 - FVIII assays and TGA (15-30 minutes after start of infusion)

At 30 \pm 5 min post-infusion:

- Vital signs (body temperature, respiratory rate, pulse rate, and supine systolic and diastolic blood pressure)

Throughout the visit, the following assessments will be carried out:

- Adverse events
- Concomitant medications and non-drug therapies

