^a Subjects transitioning from another BAX 855 study may have to repeat the PK assessment if evaluated to be necessary by the sponsor. The washout period prior to the initial PK determination is 72-96 hours, depending on the FVIII concentrate. An optional PK will also be performed at the 9-month visit (steady state PK) with the same post-infusion sampling timepoints.

^b If a subject has a bleeding episode, instead of a phone visit the subject must attend a site visit to assess FVIII trough levels and IR and re-evaluate the PK-guided regimen (see [Figure 2](#)). In these cases the subject will undergo all planned assessments for a study visit, including assessment of vital signs, physical examination, and all laboratory assessments excluding clinical chemistry and the lipid panel.

^c Including subjects who withdraw or discontinue. When planning the Completion/Termination Visit, it must be ensured that the second 6-month study period will consist of a minimum of 26 weeks and that the subject will have received his PK-tailored dosing regimen for at least 52 weeks.

^d Occurs at enrollment (prior to any study-specific procedure).

^e Medical history to include hemophilia history (confirmation of diagnosis & severity; family history of hemophilia; documentation of a mutation, if known; presence of any target joints; and historical ABR, blood group if available). Medication history to include documentation of all FVIII replacement therapies used within the last year, any prior history of use of any pegylated medication (e.g., PEG-interferon) at any time in the past, and other medications in the last 30 days.

^f Indicates that adverse events, concomitant medications, non-drug therapies, bleeding episodes and their treatment as well as the physical activity levels 8 hours prior to the occurrence of bleeding will be continuously monitored but specifically discussed and reviewed at these timepoints.

^g Includes height and weight at screening, weight at the pre-infusion assessments, and Karnofsky performance score at screening.

^h Pulse, respiration, supine blood pressure, and temperature to be assessed within 15 minutes prior to start of infusion and 30 ±5 minutes following infusion.

Continued on Next Page

Continued

- ⁱ The physical activity level in the 8 hours before the start of the bleeding episode should also be recorded.
- ^j A target joint is defined as one in which there have been ≥ 4 bleeds in any consecutive 6-month period.

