^c If a subject has a bleeding episode since the last visit before the 7.5 month ±2 week or 10.5 month ±2 week visits, instead of a phone visit the subject must attend a site visit to assess FVIII trough levels and IR and re-evaluate the PK-guided regimen. In these cases, the subject will undergo all assessments as listed for the 3 and 6 month ±2 week visits.

^d Including subjects who withdraw or discontinue. When planning the Completion/Termination Visit it must be ensured that the second 6-month study period will consist of a minimum of 26 weeks and that the subject will have received his PK-tailored dosing regimen for at least 52 weeks.

^e CD4 count is analyzed in HIV positive subjects only to determine eligibility.

^f If results of FVIII gene mutation analysis and HLA genotype are already available at the study site, they will be provided to the sponsor and an additional analysis will not be required.

^g Viral serology includes: HIV-1, HIV-2, HBcAb, HBsAb, HBsAg, HCVAb. Any HCV positive sample will be tested by PCR for viral titer.

^h If historical data on blood group type are available, this may be recorded in the CRF and blood type does not need to be determined.

Continued on Next Page

Continued

- ⁱ Pregnancy test as appropriate (serum pregnancy test in females of child-bearing potential if no urine sample is available). The pregnancy test might be repeated during the study in countries where mandated by national law.
- ^j Factor VIII assays include: 1-stage clotting FVIII activity, FVIII chromogenic activity, and FVIII antigen. For assessment of trough levels, a blood sample will be taken within 30 minutes before the IP infusion. VWF antigen level will only be determined pre-infusion at each study visit.
- ^k For assessment of FVIII IR, in addition to the pre-infusion sample a second sample will be taken 15-30 minutes after IP infusion.
- ^l Immunogenicity assessments include: inhibitory antibodies to FVIII, binding antibodies to FVIII, BAX 855 and PEG, and anti-CHO antibodies. Both IgG and IgM binding antibodies will be measured. Blood draws have to be performed within 30 min before the IP infusion.

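### The termination-visit schedule prescribes a BAX 855 infusion and expressly covers withdrawn subjects, contradicting Section 9.3, which takes subjects off treatment for severe anaphylaxis or certain inhibitors

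*Protocol*

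**What the plan says.** Section 9.3 lists events that end a subject's treatment or participation. Among them are "The subject experiences a severe anaphylactic reaction to BAX 855" and "The subject develops a confirmed high responder inhibitory antibody to FVIII" (above 5 BU). A low-responder inhibitor (0.6 to 5 BU) also qualifies if the required prophylactic dosing cannot manage it.

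These subjects are still expected at the ordinary final visit. Section 9.3 states: "Assessments to be performed at the termination visit (including in cases of withdrawal or discontinuation) are described in Section 10.6 and Section 21.3". Section 10.6 states: "Assessments to be performed at the termination visit (including in cases of withdraw or discontinuation) can be found in Section 21.2", and goes on to name Sections 21.3 and 21.4. It adds: "Every effort will be made to have discontinued subjects complete the study completion/termination visit". Footnote c of Section 21.3 and footnote d of Section 21.4 both describe the visit as "Including subjects who withdraw or discontinue".

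At that visit Section 21.2 prescribes "Infusion of PK-guided prophylactic dose of BAX 855", then FVIII and TGA sampling and vital signs after the infusion. Section 21.3 has an unbracketed X in the IP treatment row, and its footnote n says the product is given in clinic at the visits so marked. In Section 21.4 the FVIII cell for this visit carries footnote k: "For assessment of FVIII IR, in addition to the pre-infusion sample a second sample will be taken 15-30 minutes after IP infusion". Section 12.2 requires incremental recovery (IR) at every study visit except Week 4, Week 8 and Month 4.5, so the final visit is not excepted.

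**The concern.** Two instructions apply to the same subjects and cannot both be followed. Section 9.3 stops BAX 855; the schedule for the visit to which Section 9.3 sends them gives another dose. Site staff usually work from the visit flow and the schedule tables, and nothing there separates a subject who completed 52 weeks from one removed after a severe reaction to the product. The only clinical precondition stated for the visit is that the subject is not actively bleeding.

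What is at stake is safety and consistency. After severe anaphylaxis, a literal reading of the checklist would mean re-exposure. After an inhibitor, it would mean dosing a subject whom the protocol has taken off the drug. The trial's statistical conclusions are not at stake.

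**Working it through.** The contradiction involves no calculation, so the passages are set side by side.

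| Protocol section | What it directs | Exemption for Section 9.3 withdrawals? |
|---|---|---|
| 9.3 | Stops treatment or participation for severe anaphylaxis, a high-responder inhibitor or an unmanageable low-responder inhibitor; refers leavers to 10.6 and 21.3 | Not applicable |
| 10.6 | Every effort to complete the final visit; refers leavers to 21.2, 21.3 and 21.4. The paragraph on discontinuation for an AE allows extra investigations but removes none | None |
| 21.2, final visit | Infusion, then FVIII/TGA samples and vital signs | None |
| 21.3, IP treatment row, footnotes c and n | X; leavers included; product given in clinic at marked visits | None |
| 21.4, footnotes d and k | Leavers included; sample after infusion | None |
| 12.2 | IR at this visit | None |

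The protocol conditions infusions elsewhere. Section 21.2 makes the infusion at screening of transitioning subjects apply only where relevant, and it separates the Month 9 dose for an optional PK from the dose for IR alone. Section 21.3 uses (X) at Months 7.5 and 10.5. The final visit has no such qualifier.

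For how often this could arise, Section 6.5 gives the inputs:

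- 234 previously treated subjects, with no inhibitor of 0.6 BU or more and no allergic or hypersensitivity AE.
- Of these, 186 had at least 50 exposure days, 114 at least 100 and 72 at least 150. Some subjects received only a single PK dose.

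Planned exposure in this trial over 52 weeks:

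- Twice weekly: 52 × 2 = 104 exposure days.
- Every other day: 364 / 2 = 182 exposure days.

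With zero events in n subjects, the one-sided 95% upper bound is 1 − 0.05^(1/n):

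- n = 234: 1 − 0.05^(1/234) = 1.27%
- n = 114: 1 − 0.05^(1/114) = 2.59%
- n = 72: 1 − 0.05^(1/72) = 4.08%

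The bound depends on which exposure is thought comparable, and the two smaller groups are closer to this trial's dosing. The observed count is zero in each. None of these bounds is an expected number of cases. For inhibitors they also cover a wider class than Section 9.3, since a manageable low-responder inhibitor does not trigger withdrawal.

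**The case against.** The strongest reply is that Section 9.3 already governs dosing. It is the specific rule, the visit list is generic, and a subject removed from treatment has no allocated regimen and no next planned prophylactic infusion, to which Section 21.2 ties the timing of this visit. Sections 9.3 and 10.6 also speak of assessments, which Section 21.2 lists separately from the infusion. The footnotes that bring in leavers also require at least 26 weeks in the second period and 52 weeks of dosing, which an early leaver cannot meet, so the visit must be applied with judgement anyway. Sections 13.3 and 16.5 let the investigator act or deviate when there is an immediate hazard.

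Most of this stands, and it is why most investigators would withhold the dose. A reader might infer that the protocol would in practice have anaphylactic subjects re-challenged; the documents do not support that, because Section 9.3 and the hazard clauses point the other way. But the reconciliation has to be inferred. The schedule in Section 21.3 covers procedures as well as assessments and marks IP treatment X. Relying on Section 16.5 turns the correct action into a protocol deviation that must be reported to the sponsor.

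The reply also succeeds on inhibitors. A reader might treat inhibitors as carrying the same re-exposure hazard as anaphylaxis. The documents do not say so: Section 9.3 keeps low-responder subjects on BAX 855 when dosing can manage them, and Section 8.7.6 recommends an IR determination when bleeding is unexpectedly frequent or responds poorly. For inhibitors, only the contradiction with Section 9.3 remains.

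**Conclusion.** The point holds as a minor drafting contradiction with a safety aspect. The final-visit schedule prescribes an infusion for a group that expressly includes subjects whom Section 9.3 has taken off the drug. The hazard is clear for severe anaphylaxis. For high-responder and unmanageable low-responder inhibitors, the two instructions simply conflict.

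The practical size is small. No such event is reported in Section 6.5, and harm would need the subject to attend and staff to infuse despite the withdrawal. A reader might take the 1.27% from all 234 subjects as a ceiling for this trial. It is not one, because that group pools single-dose and low-exposure subjects; zero events in those with at least 100 or 150 exposure days leaves 2.59% or 4.08%. The events are rare, but the documents do not pin the rate down further.

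A reader might also suspect an effect on the trial's result. There is none: the primary analysis compares bleed-free proportions and does not use the termination IR value, and neither the power calculation nor the SAP needs to change.

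The conclusion rests on the visible text. The Study Flow Chart (Figure 2) is not shown, and the Investigator's Brochure, to which Section 8.7.2 refers for administration, is not available.

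**What to change.** In Section 21.2 under the Completion/Termination Visit, in footnote c of Section 21.3 and in footnotes d and k of Section 21.4, add a sentence to this effect: for subjects taken off treatment under Section 9.3 because of a severe anaphylactic reaction or an inhibitor, the BAX 855 infusion and the post-infusion FVIII/TGA samples and vital signs are omitted; all other termination assessments, including immunogenicity, are still done. Footnote k also serves other visits, so its addition should name the termination visit. Change X to (X) in the IP treatment row of Section 21.3 for this visit.

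The immunogenicity sample matters most in these subjects and is currently timed to the start of the infusion; the sentence keeps the sample while dropping the dose. Because the exemption applies only after withdrawal from treatment, the IR recommended in Section 8.7.6 during work-up is untouched.

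The cost is one termination IR value in the rare affected subject. Extending the exemption to everyone no longer on prophylaxis would be optional tidying and is not part of the safety fix.

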21.3 Schedule of Study Procedures and Assessments

Procedures/ Assessments	Screening Visit	PK Assessment ^a Pre infusion, 15-30 min, 3 ±0.5 h, 8 ±0.5 h, 24 ±2 h, 48 ±4 h, 72 ±4 h & 96 ±4 h Post- Infusion	Baseline Visit	Study Visits								Completion/ Termination Visit ^c 12 Mo (53 ±1 Wk)
				Visit 4Wk ±5d	Visit 8Wk ±1Wk	Visit 3 Mo ±2Wk	Visit 4.5 Mo ±2Wk	Visit 6 Mo ±1Wk (26 ±1Wk)	Phone Visit 7.5 Mo ±2Wk ^b	Visit 9 Mo ±2Wk + optional PK	Phone Visit 10.5 Mo ±2wk ^b	
Washout	N/A	72-96 h		Consistent with the infusion interval according to the treatment regimen provided to the subject and immediately before the next planned regular prophylactic infusion.								
Informed consent ^d	X											
Eligibility criteria	X											
Medical and medication history ^e	X*											
Concomitant medications ^f	X*	X	X	X	X	X	X	X	X	X	X	X
Non-drug therapies ^f	X*	X	X	X	X	X	X	X	X	X	X	X
Physical exam ^g	X*	X	X			X		X	(X) ^b	X	(X) ^b	X
Vital signs ^h	X*	X	X	X	X	X	X	X	(X) ^b	X	(X) ^b	X
Adverse events ^f	*	X	X	X	X	X	X	X	X	X	X	X
Bleeding episodes and their treatment ^{f,1}	*			X	X	X	X	X	X	X	X	X
Assessment of target joints ^j	X		X			X		X	(X)	X	(X)	X
Joint score (HJHS)			X									X
X-ray of impaired joint			X ^k	(X) ^k								
Subject diary ^l	X	X	X	X	X	X	X	X	X	X	X	X
Laboratory assessments ^m	X*	X	X	X	X	X	X	X	(X) ^b	X	(X) ^b	X
IP treatment ⁿ		X	X	X	X	X	X	X	(X) ^b	X	(X) ^b	X
IP dispense ^o	X ⁿ	(X)	X	X	X	X	X	X		X		

Procedures/ Assessments	Screening Visit	PK Assessment ^a Pre infusion, 15-30 min, 3 ±0.5 h, 8 ±0.5 h, 24 ±2 h, 48 ±4 h, 72 ±4 h & 96 ±4 h Post- Infusion	Baseline Visit	Study Visits								Completion/ Termination Visit ^c 12 Mo (53 ±1 Wk)
				Visit 4Wk ±5d	Visit 8Wk ±1Wk	Visit 3 Mo ±2Wk	Visit 4.5 Mo ±2Wk	Visit 6 Mo ±1Wk (26 ±1Wk)	Phone Visit 7.5 Mo ±2Wk ^b	Visit 9 Mo ±2Wk + optional PK	Phone Visit 10.5 Mo ±2wk ^b	
Washout	N/A	72-96 h		Consistent with the infusion interval according to the treatment regimen provided to the subject and immediately before the next planned regular prophylactic infusion.								
Re-evaluation of PK regimen/dose adjustments ^p				X	X	X	X	X	(X) ^b	(X)	(X) ^b	
PROs ^q	(X) ^r		(X)	(X) ^r	(X) ^r	(X) ^r	(X) ^r	X	(X) ^r	(X) ^r	(X) ^r	X

* The screening visit coincides with the end of study visit of the previous BAX 855 study. The procedures/assessments marked with an asterisk (*) will be transcribed from the end of study visit of the previous BAX 855 study.

^a Subjects transitioning from another BAX 855 study may have to repeat the PK assessment if evaluated to be necessary by the sponsor. The washout period prior to the initial PK determination is 72-96 hours, depending on the FVIII concentrate. An optional PK will also be performed at the 9-month visit (steady state PK) with the same post-infusion sampling timepoints.

^b If a subject has a bleeding episode, instead of a phone visit the subject must attend a site visit to assess FVIII trough levels and IR and re-evaluate the PK-guided regimen (see [Figure 2](#)). In these cases the subject will undergo all planned assessments for a study visit, including assessment of vital signs, physical examination, and all laboratory assessments excluding clinical chemistry and the lipid panel.

^c Including subjects who withdraw or discontinue. When planning the Completion/Termination Visit, it must be ensured that the second 6-month study period will consist of a minimum of 26 weeks and that the subject will have received his PK-tailored dosing regimen for at least 52 weeks.

^d Occurs at enrollment (prior to any study-specific procedure).

^e Medical history to include hemophilia history (confirmation of diagnosis & severity; family history of hemophilia; documentation of a mutation, if known; presence of any target joints; and historical ABR, blood group if available). Medication history to include documentation of all FVIII replacement therapies used within the last year, any prior history of use of any pegylated medication (e.g., PEG-interferon) at any time in the past, and other medications in the last 30 days.

^f Indicates that adverse events, concomitant medications, non-drug therapies, bleeding episodes and their treatment as well as the physical activity levels 8 hours prior to the occurrence of bleeding will be continuously monitored but specifically discussed and reviewed at these timepoints.

^g Includes height and weight at screening, weight at the pre-infusion assessments, and Karnofsky performance score at screening.

^h Pulse, respiration, supine blood pressure, and temperature to be assessed within 15 minutes prior to start of infusion and 30 ±5 minutes following infusion.

Continued on Next Page

Continued

- ⁱ The physical activity level in the 8 hours before the start of the bleeding episode should also be recorded.
- ^j A target joint is defined as one in which there have been ≥ 4 bleeds in any consecutive 6-month period.
- ^k At baseline or Week 4 ± 5 days. If an X-ray of an impaired joint evaluated as part of the HJHS is already available and not older than 12 months, it does not have to be repeated.
- ^l The subject diary will be handed out at screening and training will be provided at the subsequent visits and the entries are reviewed and discussed with subject. It will be used to document bleeds, any physical activity in the 8 hours before the bleed (see Section 8.2), treatment administered and response to BAX 855, prophylactic infusions, untoward events, concomitant medications, PROs and health resource use data, if applicable.
- ^m For laboratory assessments, See Section 21.4.
- ⁿ BAX 855 is administered in the clinic at the visits shown. At the PK assessment(s), a set dose of 60 ± 5 IU/kg BAX 855 is used; in all other cases, including the determination of IRs, the dose is PK-guided according to the allocated regimen.
- ^o Transitioning subjects will receive IP of study 261303 as of the screening visit. Newly recruited subjects will continue with their previous treatment regimen until the first prophylactic PK-guided infusion at baseline and the infusion for PK determination.
- ^p In the first 6-month period, adjustments can be made based on PK and FVIII trough levels from previous study visits. Dose adjustments in second 6-month period are only permitted when FVIII trough levels are outside of the target window. Adjustments should be based on PK, pre-dose FVIII trough level from previous visit, any change in body weight, and assessment of any spontaneous bleeds. Before any dose adjustments are performed an additional visit should be scheduled within 14 days after receipt of FVIII activity results. Details of dose adjustments will be provided in a separate document.
- ^q PROs include: Haemo-SYM Questionnaire, EQ-5D questionnaire, Short-Form 36 (SF-36), Physical Activity, and Health Resource Use; PROs can be done either at screening visit or baseline visit. Should always be completed before any study visit specific procedure.
- ^r EQ-5D, Patient Activity Level and Health Resource Use will be determined at each study visit.

